## 11.5. Cohorts for Analyses

### 11.5.1. Exposed Set

The Exposed Set (ES) will include all subjects with at least one study vaccine administration documented.

A safety analysis based on the ES will include all vaccinated subjects.

An immunogenicity analysis will be conducted on the ES and will include all vaccinated subjects for whom immunogenicity data are available.

The *ES* analysis will be performed per treatment actually administered at Dose 1.

**11.5.2. Exposed Set of subjects with a negative RSV exposure status**

The Exposed Set of subjects with a negative RSV exposure status will include all vaccinated subjects assessed as RSV unexposed at screening based on in-stream baseline serological testing.

The safety analysis of incidence of RSV-LRTI will be conducted on the cohort of subjects with a negative RSV exposure status (at screening based on in-stream baseline serological testing) as well as on the entire ES.

**11.5.3. Per-protocol Set for analysis of immunogenicity**

The per-protocol set (PPS) cohort for analysis of immunogenicity will be defined by timepoint and will consist of all subjects from the ES who complied with eligibility criteria, study procedures up to the end of the study and had immunogenicity results in the epoch as described below.

More specifically, the PPS cohort for analysis of immunogenicity up to Day 61 (Visit 5) /at Visit 7 (end of the first RSV transmission season) will include all evaluable subjects:

- Who met all eligibility criteria (i.e., no protocol violation linked to the inclusion/exclusion criteria, including age).
- Who received study vaccine as scheduled per protocol.
- For whom the administration route and site of the vaccine was as according to protocol.
- Who received the vaccine according to protocol procedures.
- Who complied with the vaccination schedule, as specified in [Table 7](#).
- Who did not receive a concomitant medication/product/vaccine leading to exclusion from a PPS analysis, as described in Section [7.6.2](#), up to Day 61 (Visit 5) /at Visit 7 (end of the first RSV transmission season).
- Who complied with the timings of the post vaccination blood sampling for immune response evaluation, up to Day 61 (Visit 5) /at Visit 7 (end of the first RSV transmission season), as specified in [Table 7](#).
- For whom post-vaccination immunogenicity results are available for at least one assay up to Day 61 (Visit 5) /at Visit 7 (end of the first RSV transmission season).

**Table 24 presents the intervals between study visits that determine subjects' eligibility for inclusion in the PPS analysis.**

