- In countries where Bexsero or Nimenrix is used as a control, two doses will be administered IM with at least a 2 month interval between these primary doses. A booster dose will be administered IM in the second year of life at Visit 7, with an interval of at least 2 months between the primary series and booster dose. The first Bexsero or Nimenrix dose will be administered at Day 1 (Visit 1) (in the groups receiving only Bexsero or Nimenrix, respectively). In the groups receiving only Bexsero or Nimenrix, the second dose will be at Day 61 (Visit 5). The first Bexsero or Nimenrix dose to be administered to the 1D and 2D RSV groups will be at Day 61 (Visit 5), following the 1 or 2 RSV vaccine doses, respectively. The second dose of Bexsero or Nimenrix in the 1D and 2D groups will be at Day 121 (Visit 6). Formulation buffer will be administered, when neither RSV vaccine nor comparator is scheduled, at the 5th vaccination visits (see Synopsis Table 3).
- In countries where *Synflorix* is used as a control, two doses will be administered IM with at least a 1 month interval between these primary doses. A booster dose will be administered IM in the second year of life at Visit 7. The first *Synflorix* dose will be administered at Day 31 (Visit 3) (in the group receiving only *Synflorix*). In the group receiving only *Synflorix*, the second dose will be at Day 61 (Visit 5). The first *Synflorix* dose to be administered to the 1D and 2D RSV groups will be at Day 61 (Visit 5), following the 1 or 2 RSV vaccine doses, respectively. The second dose of *Synflorix* in the 1D and 2D groups will be at Day 121 (Visit 6). Formulation buffer will be administered, when neither RSV vaccine nor comparator is scheduled, at the 5 vaccination visits (see Synopsis Table 3).
- In countries where Menveo is used as a control, two doses will be administered IM at least 3 months apart with the second dose in the second year of life at Visit 7. The first Menveo dose will be administered at Day 31 (Visit 3) (in the group receiving only Menveo). The first Menveo dose to be administered to the 1D and 2D RSV groups will be at Day 61 (Visit 5),

following the 1 or 2 RSV vaccine doses, respectively. Since the second Menveo dose has to be administered in the second year of life at Visit 7, no administration will be performed at Day 121 (Visit 6). Formulation buffer will be administered, when neither RSV vaccine nor comparator is scheduled, at the 4 vaccination visits (see Synopsis Table 3).

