Solicited adverse event:	AEs to be recorded as endpoints in the clinical study. The presence/occurrence/intensity of these events is actively solicited from the subject or an observer during a specified post-vaccination follow-up period.
Study vaccine/product	Any investigational vaccine/product being tested and/or any authorized use of a vaccine/ product as a reference or administered concomitantly, in a clinical trial that evaluates the use of an investigational vaccine/product.
Subject:	Term used throughout the protocol to denote an individual who has been contacted in order to participate or participates in the clinical study, either as a recipient of the vaccine(s) or as a control.
Subject number:	A unique number identifying a subject, assigned to each subject consenting to participate in the study.
Treatment:	Term used throughout the clinical study to denote a set of investigational product(s) or marketed product(s) intended to be administered to a subject.
Treatment number:	A number identifying a treatment to a subject, according to treatment allocation.
Unsolicited adverse event:	Any AE reported in addition to those solicited during the clinical study. Also any 'solicited' symptom with onset outside the specified period of follow-up for solicited symptoms will be reported as an unsolicited adverse event.

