## Comparator or Placebo:

- In countries where *Bexsero or Nimenrix* is used as a control, two doses will be administered IM with at least a 2 month interval between these primary doses. A booster dose will be administered IM in the second year of life at Visit 7, with an interval of at least 2 months between the primary series and booster dose. The first *Bexsero or Nimenrix* dose will be administered at Day 1 (Visit 1) (in the groups receiving only *Bexsero or Nimenrix*, respectively). In the groups receiving only *Bexsero or Nimenrix*, the second dose will be at Day 61 (Visit 5). The first *Bexsero or Nimenrix* dose to be administered to the 1D and 2D RSV groups will be at Day 61 (Visit 5), following the 1 or 2 RSV vaccine doses, respectively. The second dose of *Bexsero or Nimenrix* in the 1D and 2D groups will be at Day 121 (Visit 6). Formulation buffer will be administered, when neither RSV vaccine nor comparator is scheduled, at the 5 vaccination visits (see [Figure 1](#) and [Table 2](#)).
- In countries where *Synflorix* is used as a control, two doses will be administered IM with at least a 1 month interval between these primary doses. A booster dose will be administered IM in the second year of life at Visit 7. The first *Synflorix* dose will be administered at Day 31 (Visit 3) (in the group receiving only *Synflorix*). In the group receiving only *Synflorix*, the second dose will be at Day 61 (Visit 5). The first *Synflorix* dose to be administered to the 1D and 2D RSV groups will be at Day 61 (Visit 5), following the 1 or 2 RSV vaccine doses, respectively. The second dose of *Synflorix* in the 1D and 2D groups will be at Day 121 (Visit 6). Formulation buffer will be administered, when neither RSV vaccine nor comparator is scheduled, at the 5 vaccination visits (see [Figure 1](#) and [Table 2](#)).

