  - Blood samples for **humoral immunogenicity** will be taken from all subjects at Screening and on Day 31, Day 61, and at the visit occurring at the end of the first RSV transmission season.
  - Blood sample for **assessment of mechanism of illness (potential ERD)** will be taken from subjects hospitalized for LRTI (only for RSV-positive subjects using a locally available RSV test).
  - Nasal swab: there will be monthly nasal swab to detect asymptomatic RSV infections during the RSV season and if following active or a passive surveillance contacts, a subject presents symptoms of RTI, a nasal swab will be collected (as well as a sample for local testing i.e., the type of sample to be determined locally [e.g., swab, etc.]) (Refer to the SPM).
- Study visits: Other than the screening visit and assessment visits for active/passive surveillance, there will be 8 study visits except in countries where *Menveo* or Placebo is used as a control where there will be 7 study visits.
  - In countries where *Menveo* is used as a comparator, no administration will be performed at Day 121 and therefore in those countries there will be no Visit 6 and it will be administered at the end of the first RSV season at Visit 7 (refer to [Table 2](#) and [Table 7](#)).
  - In countries where Placebo is used as a control, no vaccine administration will be performed after Visit 3 and therefore in those countries there will be no Visit 6. There will be a Visit 5 and Visit 7 for countries using Placebo and all other study procedures will occur at these visits except vaccination.

- Visit 2 (Day 8), Visit 4 (Day 38), and Visit 8 (no blood sampling for immune response and no vaccine administration) may take place in the subject's home or at the investigators clinical facility as appropriate to the circumstances in the judgment of the investigator.
  - For authorized sites only, Visit 5 (Day 61) and Visit 7 (both with blood sampling) may also take place in the subject's home or at the investigators clinical facility as appropriate to the circumstances in the judgment of the investigator.
- Type of study: self-contained.
- Data collection: electronic Case Report Form (eCRF).
- Safety monitoring: internal safety review committee (iSRC) and IDMC (refer to Section 9.10).
- Surveillance for RSV-RTI, difficulty in breathing, and wheezing episodes.

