**Table 24 Maximum allowed interval between study visits (Amended 1 August 2019)**

Interval	Allowed length of interval
Screening → Visit 1 (Day 1)	0 - 30 days
Visit 1 (Day 1) → Visit 2 (Day 8)	7 - 10 days
Visit 1 (Day 1) → Visit 3 (Day 31)	23 - 44 days 
Visit 1 (Day 1) → Visit 5 (Day 61)	60 - 81 days 
Visit 3 (Day 31) → Visit 4 (Day 38)	7 - 10 days
Visit 3 (Day 31) → Visit 5 (Day 61) 	30 - 37 days 
Visit 5 (Day 61) → Visit 6 (Day 121) 	60 - 81 days
Visit 7 (end of the first RSV transmission season)	Defined end of first RSV transmission season 
Visit 8 (end of the second RSV transmission season)	Defined end of second RSV transmission season 

 Subjects will not be eligible for inclusion in the PP cohort for analysis of immunogenicity if they make the study visit outside this interval.

 Where *Synflorix* is used as the comparator, a minimum of 30 days between Visit 3 and Visit 5 must be maintained to align with the active comparator vaccination schedule.

 The interval between Visit 1 and Visit 5 must be a minimum of 60 days to be in line with the active comparator vaccination schedules as per the respective approved labels.

 In countries where *Menveo* or Placebo is used as a comparator, no administration will be performed at Day 121 and therefore in those countries there will be no Visit 6 and *Menveo* will be administered at the end of the first RSV season at Visit 7 (refer to Table 2 and Table 7).

 As soon as possible after the end of the RSV season (approximately within 4 weeks) and in accordance with the active comparator vaccination schedule if applicable. If the active comparator dosing for V7 is later than 4 weeks after the end of the first RSV transmission season, then the recommended timing of the active comparator takes precedence.

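### The Visit 7 immunogenicity per-protocol set can drop infants with complete Visit 1 and 3 injections because of a missed comparator or buffer injection at Visit 5 or 6

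*Protocol*

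**What the plan says.** Section 11.5.3 gives one list of criteria for the PPS up to Day 61 and at Visit 7. Four of them concern vaccination. An infant must be one "Who received study vaccine as scheduled per protocol", must have had the protocol's route and site, must have been vaccinated by protocol procedures, and must be one "Who complied with the vaccination schedule, as specified in" Table 7. None of the four is limited to the RSV vaccine or to particular visits.

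The glossary defines study vaccine/product as "Any investigational vaccine/product being tested and/or any authorized use of a vaccine/ product as a reference or administered concomitantly". Table 15, the table of study vaccines, lists the two ChAd155-RSV presentations, formulation buffer, placebo and all four comparators.

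Table 7 marks vaccine administration at Visits 1, 3, 5, 6 and 7. RSV dosing ends at Visit 1 (1D) or Visit 3 (2D), and later injections are comparator or buffer. For the Bexsero, Nimenrix and Synflorix countries, Section 3 states: "Formulation buffer will be administered, when neither RSV vaccine nor comparator is scheduled, at the 5 vaccination visits". Menveo countries have no Visit 6. For Placebo countries it states: "In countries where Placebo is used as a control, no vaccine administration will be performed after Visit 3".

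Table 24, footnote 1, reads: "Subjects will not be eligible for inclusion in the PP cohort for analysis of immunogenicity if they make the study visit outside this interval". It is attached to the Visit 1 to 3, Visit 1 to 5 and Visit 3 to 5 intervals only. Section 11.9 makes the PPS the primary immunogenicity set and gives the last time point its own PPS.

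**The concern.** The Visit 7 endpoints are RSV-A neutralizing titre and RSV F antibody concentration. What an infant must have received for these to be interpretable is the Visit 1 and Visit 3 course: RSV vaccine, or the matching control injections. By the compositions in Table 15, the later products contain no RSV antigen, so a missed dose of one is not expected to change RSV antibody.

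The protocol foresees infants who stop vaccination but stay in follow-up. Section 10.2.2 allows continued immunogenicity follow-up after withdrawal from study vaccine, and Section 9.10.5 stops all vaccination during a hold while immunology procedures continue. As 11.5.3 is written, such infants can fail the Visit 7 PPS although their RSV course was complete.

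The rule also sits badly with Table 24. Under that table, a Visit 6 injection given well outside its interval carries no PPS exclusion. Under 11.5.3, the same injection missed altogether, or given by a deviating route, site or procedure, does exclude.

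At stake are some valid Visit 7 titres in the primary immunogenicity set, and an exclusion pattern that depends on which comparator a country chose.

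**Working it through.** No stated sample size, power or alpha rests on this set, so there is no figure of the plan to reproduce. The check is a reading of the text, followed by an illustration of size.

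**Which injections count.** From Table 2, the injections after Visit 3 and before Visit 7 are:

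| Country comparator | Injections | Visits |
|---|---|---|
| Bexsero, Nimenrix, Synflorix | 2 | 5 and 6 |
| Menveo | 1 | 5 |
| Placebo | 0 | none |

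Within a country, all three arms are injected at the same visits. The text does not settle whether the Visit 7 dose counts for the Visit 7 sample, so it is left out here.

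**What other text limits.** Footnote 1 of Table 24 governs visit intervals. It does not restrict the four vaccination criteria. It does remove infants whose Visit 5 falls outside its windows, whatever 11.5.3 says about the Visit 5 injection. Section 7.3 only prefers the left side, so use of the other leg is not in itself a deviation.

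**Size.** The protocol gives no miss rate. Assume a chance *m* that each injection is missed or deviates, independently between injections:

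- share excluded = 1 − (1 − *m*)^*k*, for *k* injections
- widening of a log-titre interval ≈ 1/√(share kept) − 1

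| *m* | *k* = 1: excluded | wider by | *k* = 2: excluded | wider by |
|---|---|---|---|---|
| 2% | 2.0% | 1.0% | 1 − 0.98² = 4.0% | 2.0% |
| 5% | 5.0% | 2.6% | 1 − 0.95² = 9.8% | 5.3% |
| 10% | 10.0% | 5.4% | 1 − 0.90² = 19.0% | 11.1% |

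The *k* = 1 columns describe a two-injection country where Visit 5 losses come mainly from late or missed visits. Table 24 already removes those infants, so only Visit 6 matters. The *k* = 2 columns are the upper case. If all 50 infants of a group were in two-injection countries, that case would be 50 × 0.0396 = 2.0, 50 × 0.0975 = 4.9 or 50 × 0.19 = 9.5 infants. Menveo and Placebo countries in the pooled group lower these counts.

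**Against the 10% trigger in Section 11.9.** With *k* = 2, this cause alone passes 10% only when *m* exceeds 1 − √0.9 = 5.1%.

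**The case against.** A per-protocol set is by definition restricted to those who followed the protocol, and requiring the full assigned course is an ordinary choice. Elimination codes, which decide what each missed dose does at each time point, usually belong to the SAP. That has some force, but here the protocol itself states the criteria and states them without limit. Section 11.5.3 also asks for compliance to the end of the study, whereas the glossary's PPS entry stops at the time point of analysis. Resolving that in favour of the glossary would still leave Visits 5 and 6 inside the Visit 7 horizon.

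Four stronger readings are tempting, and the documents do not support them:

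- **Bias between arms.** At Visit 6, RSV recipients receive active comparator and controls receive buffer, so a reader might infer differential exclusion. But injection visits are matched across arms within a country, parents stay blinded, and investigators have no access to allocation except in emergency unblinding. Allocation is stratified by comparator grouping and minimized on country. No arm bias is shown.
- **Loss of the titres.** Section 11.5.1 plans an immunogenicity analysis on the Exposed Set without condition. Section 11.9 adds one when more than 10% are excluded in a pooled group, and 11.9.1.1 adds one in infants with negative exposure status. The titres are retained. The Exposed Set is not a full substitute, because it also admits infants with incomplete RSV dosing.
- **Every dose must be on time.** Table 24 attaches no PPS exclusion to Visit 6 or Visit 7 timing.
- **The later injections cannot affect RSV antibody.** The protocol gives compositions and no such statement. Not expected to is as far as the text goes.

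It is also true that infants who leave before Visit 7 have no Visit 7 titre to lose, and that immunogenicity is secondary and descriptive. The power statement on enhanced disease in Section 11.4 does not use this set.

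**Conclusion.** The point holds as a cheap improvement to the wording. On the literal text, the four vaccination criteria reach the comparator and buffer injections at Visits 5 and 6, and possibly Visit 7, so an infant with complete Visit 1 and 3 injections can be dropped from the primary Visit 7 immunogenicity set.

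The consequence is a modest loss of precision that differs by comparator country, with none after Visit 3 in Placebo countries. The range runs from intervals about 1% wider (one injection, 2% missed) to about 11% wider (two injections, 10% missed). It rests entirely on assumed, independent miss rates. A hold on vaccination would break the independence assumption, because many infants would miss injections together. No conclusion about enhanced RSV disease or the primary safety objective is affected.

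**What to change.** In Section 11.5.3, state that for both the Day 61 and the Visit 7 PPS the vaccination criteria (receipt as scheduled, route and site, procedures, Table 7 schedule) apply only to the injections at Visits 1 and 3, and identically in all arms. State the reason as well. The Visit 3 buffer in the 1D groups is kept as a requirement deliberately, so that the blinded arms are held to the same rule, although it means that a 1D infant who misses only that buffer is still excluded. Leave the concomitant-product criterion, the Table 24 intervals and the blood-sampling windows unchanged.

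The cost is one sentence and the matching elimination codes. The downside is that the PPS would no longer certify compliance with the comparator course, which no RSV antibody endpoint needs. This changes membership of an analysis set only. It changes nothing in the vaccination schedule.

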**Table 24 Maximum allowed interval between study visits (Amended 1 August 2019)**

Interval	Allowed length of interval
Screening → Visit 1 (Day 1)	0 - 30 days
Visit 1 (Day 1) → Visit 2 (Day 8)	7 - 10 days
Visit 1 (Day 1) → Visit 3 (Day 31)	23 - 44 days 
Visit 1 (Day 1) → Visit 5 (Day 61)	60 - 81 days 
Visit 3 (Day 31) → Visit 4 (Day 38)	7 - 10 days
Visit 3 (Day 31) → Visit 5 (Day 61) 	30 - 37 days 
Visit 5 (Day 61) → Visit 6 (Day 121) 	60 - 81 days
Visit 7 (end of the first RSV transmission season)	Defined end of first RSV transmission season 
Visit 8 (end of the second RSV transmission season)	Defined end of second RSV transmission season 

 Subjects will not be eligible for inclusion in the PP cohort for analysis of immunogenicity if they make the study visit outside this interval.

 Where *Synflorix* is used as the comparator, a minimum of 30 days between Visit 3 and Visit 5 must be maintained to align with the active comparator vaccination schedule.

 The interval between Visit 1 and Visit 5 must be a minimum of 60 days to be in line with the active comparator vaccination schedules as per the respective approved labels.

 In countries where *Menveo* or Placebo is used as a comparator, no administration will be performed at Day 121 and therefore in those countries there will be no Visit 6 and *Menveo* will be administered at the end of the first RSV season at Visit 7 (refer to Table 2 and Table 7).

 As soon as possible after the end of the RSV season (approximately within 4 weeks) and in accordance with the active comparator vaccination schedule if applicable. If the active comparator dosing for V7 is later than 4 weeks after the end of the first RSV transmission season, then the recommended timing of the active comparator takes precedence.

#### 11.5.4. Pooled groups in the study

All subjects in the single dose (1D,  $1.5 \times 10^{10}$  vp) RSV + comparator vaccine groups will be pooled together as the pooled 1D RSV group, similarly, all subjects in the two dose (2D,  $5 \times 10^{10}$  vp) RSV + comparator vaccine groups will be pooled together as the pooled 2D RSV group, and all subjects in the comparator/Placebo control vaccine alone groups will be pooled together as the pooled comparator group ([Table 25](#)).

**Table 25 Pooled groups**

Study groups	Pooled groups
1D RSV + Bexsero	Pooled 1D RSV
1D RSV + Nimenrix	
1D RSV + Synflorix	
1D RSV + Menveo	
1D RSV + Placebo	
2D RSV + Bexsero	Pooled 2D RSV
2D RSV + Nimenrix	
2D RSV + Synflorix	
2D RSV + Menveo	
2D RSV + Placebo	
Bexsero	Pooled comparator
Nimenrix	
Synflorix	
Menveo	
Placebo	

1D: 1 Dose ( $1.5 \times 10^{10}$  vp/dose); RSV: ChAd155-RSV vaccine; 2D: 2 Dose ( $5 \times 10^{10}$  vp/dose)

